1. INTRODUCTION

This is a Phase 2, multicenter, open-label, single-arm study to assess the safety of 15 mg QD INCB054707 over 8 weeks in men and women aged 18 to 75 years with moderate to severe HS with a targeted enrollment of up to 10 participants.

The study will consist of a screening period of up to 28 days; an 8-week, open-label, single-arm treatment period; and a 4-week safety follow-up period. The estimated total duration of study participation is approximately 16 weeks for each participant.

Safety assessments include monitoring of AEs, clinical laboratory tests, vital signs, ECGs, and physical examinations. Efficacy assessments include HiSCR as assessed by the AN count, HS Pain NRS, modified Sartorius scale, draining fistula count, and need for rescue lesional treatment. Quality of life will be assessed using the DLQI (participant-reported). The purpose of this SAP is to provide details of the statistical analyses that have been outlined in the Study INCB 54707-202 Protocol.

2. STUDY INFORMATION, OBJECTIVES, AND ENDPOINTS

2.1. Protocol and Case Report Form Version

This SAP is based on INCB 54707-202 Protocol Amendment 1 dated 19 JUL 2018 and CRFs approved 20 JUN 2018. Unless superseded by an amendment, this SAP will be effective for all subsequent Protocol amendments and CRF versions.

2.2. Objectives and Endpoints

Table 1 presents the objectives and endpoints.

Table 1: Objectives and Endpoints

Objectives	Endpoints
Primary	
To evaluate the safety and tolerability of INCB054707.	• Frequency duration, and severity of AEs, clinical laboratory test results, vital signs results, ECGs, and physical examination findings.
Secondary	
• To evaluate the systemic exposure to INCB054707.	Population PK parameters of INCB054707.
• To evaluate the efficacy of INCB054707.	Proportion of participants with a HiSCR at each visit.
	• Proportion of participants achieving an AN count of 0 to 2 at each visit.
	 Mean change from baseline in the HS Pain NRS scores, worst and average pain, at each visit.
	 Mean change from baseline to Week 8 in the modified Sartorius scale score.
	 Mean change from baseline in the number of draining fistulas count at each visit.
	• Proportion of participants at each category of Hurley Stage at baseline and Week 8.
	• Proportion of participants with change from baseline in Hurley Stage at Week 8.
	 Proportion of participants in each HS-PGIC category during the treatment period.
To assess the need for rescue lesional treatment.	Proportion of participants requiring rescue lesional treatment.
	• Number of interventions with rescue lesional treatment.
To assess patient-reported quality of life burden.	Proportion of participants at each scoring category of DLQI at each visit.

3. STUDY DESIGN

This is a Phase 2, multicenter, open-label, single-arm study to assess the safety of 15 mg QD INCB054707 over 8 weeks in men and women aged 18 to 75 years with moderate to severe HS with a targeted enrollment of up to 10 participants. Safety assessments include monitoring of AEs, clinical laboratory tests, vital signs, ECGs, and physical examinations. Efficacy assessments include HiSCR as assessed by the AN count, HS Pain NRS, modified Sartorius scale, draining fistula count, and need for rescue lesional treatment. Quality of life will be assessed using the DLQI (participant-reported).

Optional medical photographs of a target lesion will be taken at selected anatomic sites to illustrate the outcome of the study.

3.1. Randomization

Not applicable.

3.2. Control of Type I Error

All statistical analyses are exploratory in nature. No alpha control will be implemented. Unless otherwise specified, all confidence intervals provided will be at the 95% confidence level.

3.3. Sample Size Considerations

The sample size was based on the precedent of other safety and PK studies and was not based on statistical power calculations.

3.4. Schedule of Assessments

Refer to Protocol Amendment 1 dated 19 JUL 2018 for a full description of all study procedures and assessment schedules for this study.

4. DATA HANDLING DEFINITIONS AND CONVENTIONS

4.1. Scheduled Study Evaluations

4.1.1. Day 1

Day 1 is the date that the first dose of study drug INCB054707 is administered to the participants.

4.1.2. Study Day

If a visit/reporting date is on or after Day 1, then the study day at the visit/reporting date will be calculated as

Day
$$\# = (Visit/Reporting Date - Day 1 date + 1).$$

If the visit/reporting date is before Day 1, then the study day at the visit/reporting date will be calculated as

$$\text{Day } \# = (\text{Visit/Reporting Date} - \text{Day 1 date}).$$

A study day of -1 indicates 1 day before Day 1.

4.1.3. Baseline Value

Baseline is the last nonmissing measurement obtained before the first administration of INCB054707.

When scheduled assessments and unscheduled assessments occur on the same day and time of the assessment or time of first dose is not available, use the following convention to determine baseline:

- If both a scheduled and an unscheduled visit are available on the day of the first dose and the time is missing, use the scheduled assessment as baseline.
- If all scheduled assessments are missing on the day of the first dose and an unscheduled assessment is available, use the unscheduled assessment as baseline.

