4.2. Overall Study Duration

The study will consist of a screening period of up to 28 days, an 8-week open-label, single-arm treatment period, and a 4-week safety follow-up period. The estimated total duration of study participation is approximately 16 weeks for each participant.

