8.2.5. Hidradenitis Suppurativa Pain Numeric Rating Scale

The HS Pain NRS (see Appendix F) will be completed in a daily diary by participants from screening through EOS. An 11-point scale will be used to assess the worst skin pain and the average skin pain due to HS. Ratings for the 2 items range from 0 (no skin pain) to 10 (skin pain as bad as you can imagine). Assessments will be recorded before bedtime or midnight (whichever comes first) and will be based on a recall period of the last 24 hours.

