10.3.2. Efficacy Analyses

Efficacy analyses will be conducted using the FAS. The baseline value for a variable will be defined as the last nonmissing value for this variable before or on Day 1, unless otherwise specified.

Categorical variables, including proportions of participants achieving HiSCR, with an AN count of 0 to 2, requiring rescue lesional treatment, and with a change in Hurley Stage, will be summarized using descriptive statistics including sample size, frequency, and percentages. Mean, change from baseline, and percentage change from baseline in HS pain NRS, modified Sartorius scale, and DLQI scores will be summarized using descriptive statistics, including sample size, mean, median, standard deviation, standard error of the mean, minimum, and maximum.

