7.1.5. Hidradenitis Suppurativa Pain Numeric Rating Scale

The HS Pain NRS will be completed in a daily diary by participants from screening through EOS. An 11-point scale will be used to assess the worst skin pain and the average skin pain due to HS based on a recall period of the last 24 hours. Ratings for the 2 items range from 0 (no skin pain) to 10 (skin pain as bad as you can imagine).

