7.2. Analysis of Efficacy Endpoints

The efficacy endpoints include:

- Proportion of participants with a HiSCR (at least 50% reduction in AN count with no increase in abscess count and no increase in draining fistula count relative to baseline) at each visit;
- Proportion of participants achieving an AN count of 0 to 2 at each visit;
- Mean change from baseline in the HS Pain NRS scores, worst and average pain, at each visit;
- Mean change from baseline to Week 8 in the modified Sartorius scale score;
- Mean change from baseline in the number of draining fistulas count at each visit;
- Proportion of participants at each category of Hurley Stage at baseline and Week 8;
- Proportion of participants with change from baseline in Hurley Stage at Week 8;
- Proportions of participants in each HS-PGIC category during the treatment period.
- Proportion of participants requiring rescue lesional treatment;

- Number of interventions with rescue lesional treatment;
- Proportion of participants at each scoring category of DLQI at each visit;

Category variables will be summarized using descriptive statistics, including sample size, frequency, and percentages. Continuous variables will be summarized using descriptive statistics, including sample size, mean, median, standard deviation, standard error of the mean, minimum, and maximum.

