1.5 Others			
1.5.1	Summary of General Medical History	FAS	
1.5.2	Summary of Protocol Deviation	FAS	
Efficacy			
2.1.1	Summary of Participants With a HiSCR by Visit	FAS	
2.1.2	Summary of Participants Achieving an AN Count of 0 to 2 by Visit	FAS	
2.1.3.1	Summary of HS Pain NRS Score From Baseline to Week 12 (Worst Pain)	FAS	
2.1.3.2	Summary of HS Pain NRS Score From Baseline to Week 12 (Average Pain)	FAS	
2.1.4	Summary of Modified Sartorius Scale Score From Baseline to Week 8	FAS	
2.1.5	Summary of Draining Fistulas Count From Baseline to Week 12	FAS	
2.1.6.1	Summary of Hurley Stage at Baseline and Week 8	FAS	
2.1.6.2	Summary of Hurley Stage Change from Baseline to Week 8	FAS	
2.1.7	Summary of HS-PGIC Category by Visit	FAS	
2.1.8	Summary of Participants Requiring Rescue Lesional Treatment by Visit	FAS	
2.1.9	Summary of Interventions With Rescue Lesional Treatment by Visit	FAS	
2.1.10.1	Summary of DLQI Category by Visit	FAS	
2.1.10.2	Summary of DLQI From Baseline to Week 12	FAS	
2.1.13	Summary of Daily Analgesic Usage	FAS	

Table No.	Title	Population	
Safety			
	Drug Exposure	T	
3.1.1	Summary of Drug Compliance	FAS	
3.1.2	Summary of Study Drug Exposure	FAS	
3.2 Advers	e Events		
3.2.1	Overall Summary of Treatment-Emergent Adverse Events	FAS	
3.2.2	Summary of Treatment-Emergent Adverse Events by MedDRA System Organ Class and Preferred Term		
3.2.3	Summary of Treatment-Emergent Adverse Events by MedDRA Preferred Term in Decreasing Order of Frequency		
3.2.4	Summary of Treatment-Emergent Adverse Events by MedDRA System Organ Class, Preferred Term, and Maximum Severity		
3.2.5	Summary of Grade 3 or 4 Treatment-Emergent Adverse Events by MedDRA System Organ Class and Preferred Term		
3.2.6	Summary of Treatment-Related Adverse Events by MedDRA System Organ Class and Preferred Term		
3.2.7	Summary of Treatment-Related Adverse Events by MedDRA Preferred Term in Decreasing Order of Frequency		
3.2.8	Summary of Treatment-Related Adverse Events by MedDRA System Organ Class, Preferred Term, and Maximum Severity		
3.2.9	Summary of Grade 3 or 4 Treatment-Related Treatment-Emergent Adverse Events by MedDRA System Organ Class and Preferred Term		
3.2.9.1	Summary of Grade 3 or higher TEAE by PT in Decreasing Order of Frequency	FAS	
3.2.10	Summary of Treatment-Emergent Adverse Events Leading to Death by MedDRA System Organ Class and Preferred Term		
3.2.11	Summary of Treatment-Emergent Serious Adverse Events by MedDRA System Organ Class and Preferred Term		

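### The SAP's only visible baseline rule turns the daily pain diary into a one-entry baseline, and the visible text does not define the visit value; define both as diary means

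*SAP*

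**What the plan says.** - **Collection.** SAP 7.1.5: "The HS Pain NRS will be completed in a daily diary by participants from screening through EOS". There are two items, worst and average skin pain, each scored 0 to 10 with 24-hour recall. Protocol 8.2.5 places the entry in the evening, by bedtime or midnight.
- **Endpoint.** SAP 7.2: "Mean change from baseline in the HS Pain NRS scores, worst and average pain, at each visit". The planned pain tables in SAP Appendix A run from baseline to Week 12 and mention no averaging.
- **Baseline, SAP 4.1.3.** "Baseline is the last nonmissing measurement obtained before the first administration of INCB054707". The rule covers all variables. SAP 7.1.5, SAP 7.2 and the table list give no exception for pain.
- **Baseline, Protocol 10.3.2.** The "last nonmissing value for this variable before or on Day 1, unless otherwise specified".
- **Visit value.** Neither document visibly gives a diary window, a mean or a minimum number of entries. For laboratory tests, by contrast, SAP 8.3.2 does say which record to use when several fall in one visit window.
- **Status.** Pain is a secondary endpoint. SAP 7 calls all efficacy analyses exploratory and plans no p-values.

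**The concern.** One evening's pain score carries day-to-day noise that says nothing about treatment. Under the general rule that noise enters every participant's baseline, and so every change score at every visit. The diary already holds the data that would reduce it.

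At the visit end the difficulty is a different one. Several entries are certain to exist around each visit, and no visible rule chooses among them. In an open-label study that leaves the choice to be made during programming, after the data can be seen.

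The stakes are modest but real. Enrolment is up to 10 participants, and Protocol 2.2.1 expects the results to inform a dose-ranging Phase 2b study.

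**Working it through.** The plan states no SD, precision or power figure for pain, so there is nothing to reproduce. The check has two parts.

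**1. Entries used at baseline.** Screening lasts up to 28 days (Protocol 4.2). The rule keeps 1 entry, so up to 27 of 28 (96%) do not enter the baseline.

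**2. SE of mean change, n = 10.** Let Sw be the within-person day-to-day SD, St the SD of true individual change, and V the variance of a seven-day mean relative to one entry. With lag-1 autocorrelation ρ:

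V = [7 + 2·Σ(7−k)ρᵏ, k = 1 to 6] / 49

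This gives 0.143, 0.240, 0.423 and 0.641 for ρ = 0, 0.3, 0.6 and 0.8.

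- One entry at both ends: SE = √[(St² + 2Sw²)/10]
- Mean at one end only: SE = √[(St² + Sw²(1 + V))/10]
- Mean at both ends: SE = √[(St² + 2Sw²V)/10]

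Assumed ranges, none of them from the documents: Sw 1 to 2 points, St 1 to 2 points, ρ 0 to 0.8.

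Middle case (Sw 1.5, St 2, ρ 0.3):

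- One entry at both ends: √[(4 + 4.5)/10] = √0.850 = 0.92
- Mean at baseline only: √[(4 + 2.25 × 1.240)/10] = √0.679 = 0.82
- Mean at both ends: √[(4 + 4.5 × 0.240)/10] = √0.508 = 0.71

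| Case | Sw, St, ρ | One entry at both ends | Mean at baseline only | Mean at both ends | Reduction, both ends |
|---|---|---|---|---|---|
| Least gain | 1, 2, 0.8 | 0.77 | 0.75 | 0.73 | 6% |
| Middle | 1.5, 2, 0.3 | 0.92 | 0.82 | 0.71 | 23% |
| Largest gain | 2, 1, 0 | 0.95 | 0.75 | 0.46 | 51% |

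The baseline-only entries in the outer rows are √[(4 + 1 × 1.641)/10] = 0.75 and √[(1 + 4 × 1.143)/10] = 0.75. Averaging baseline alone therefore lowers the SE by about 3%, 11% and 21% in the three rows.

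The formula for a mean at one end is symmetric in the two ends, so the middle case can also be read the other way. If visit values turn out to be seven-day means already, the one-entry baseline leaves the SE at 0.82 where 0.71 was available. The baseline rule costs precision however visits are handled.

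For scale, the middle-case 95% half-width (t on 9 df, 2.262) falls from 2.09 to 1.61 points with means at both ends. Single entries would need about 10 × 8.5/5.08 ≈ 17 participants for the same SE.

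The formulas treat day-to-day errors at the two ends as independent. That is reasonable for windows weeks apart and less so for Week 1 at high ρ.

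**The case against.** - **Most of the diary is discarded.** A reader might infer this. One entry at baseline and one at each of six post-baseline visits would be 7 of about 112 diary days (28 + 56 + 28), or 6%. The documents do not support it: they never say a visit uses one entry. Protocol Table 3 marks the pain row with a footnote e whose text is not readable in the copy reviewed, and the diary appendix (Appendix F) is not in that copy either. Either could define a window. A listing of pain scores is also planned. Only the one-entry baseline is established.
- **A post-dose Day 1 entry could serve as baseline.** The Day 1 dose follows that visit's blood draws (Protocol 8.1.3) and the diary is completed in the evening, so "last nonmissing value for this variable before or on Day 1" taken alone would admit it. SAP 4.1.3 excludes it, and the protocol sentence gives way to a more specific rule. The two texts should be aligned for the diary, but the analysis is not left with a post-dose baseline.
- **Same-day rescue is credited to study drug.** A visit-day evening entry does follow any rescue done at that visit. With 24-hour recall, however, a worst-pain score still covers the hours before it. Averaging does not remove carry-over from earlier rescue either: after rescue at Week 1, most of the Week 2 window follows it. This is not a reason for averaging.
- **The size is assumed and little depends on it.** Both are true. Stable disease is an entry criterion, so high autocorrelation is plausible, and the gain may sit near the low end. SAP 7.2 plans an SE for pain change but no confidence interval, so the SE is the relevant measure. No primary conclusion changes.
- **A minimum count could cost participants.** This stands. Screening has no minimum length and SAP 4.1.5 imputes nothing by default, so the rule needs a fallback.

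**Conclusion.** The point holds in a limited form. The visible SAP gives pain a one-entry baseline and leaves the visit value undefined. A multi-day mean is the more precise choice, and the data for it are already collected.

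The gain is about 6% to 51% of the SE when one entry at both ends is replaced by means at both, and about 3% to 21% for the baseline alone if visits stay at one entry. All of these figures rest on the assumed SDs and autocorrelation. The visit-end part is conditional on what Table 3 footnote e says.

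The effect is confined to a descriptive secondary endpoint; the primary safety analysis is untouched, and there is no power or alpha to change. It is an inexpensive improvement that should be made, and it does not block the study.

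**What to change.** In SAP 4.1.3 and 7.1.5, for worst and average pain separately:

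- **Baseline:** the mean of diary entries in the 7 days before Day 1, with at least 4 nonmissing. Otherwise use the mean of the available pre-dose entries, and flag the participant.
- **Visit value:** the mean of the 7 diary days before the visit date. For Week 1 (visit window ±1 day), limit this to days after the first dose so that an early visit draws in no pre-dose entry.
- **Consistency:** reconcile both definitions with Protocol 10.3.2 and with Table 3 footnote e, and record the pain-specific rule in SAP 10.1, which now lists no change from the protocol-defined analyses.

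The cost is SAP wording and simple programming, with no new data or visits. There are two downsides. The Week 1 value becomes an average over the first treatment week, which blurs a fast onset. Carry-over from earlier rescue also remains in the means and should be noted when the results are read. The seven-day window and four-entry minimum are conventions; what matters is that they are fixed before the data are summarised.

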4.1.4. Last Available Value

The last available value is the last nonmissing measurement obtained after starting INCB054707 and within 30 days after the last dose of INCB054707.

4.1.5. Handling of Missing and Incomplete Data

In general, values for missing data will not be imputed unless methods for handling missing data are specified in relevant sections.

4.2. Variable Definitions

4.2.1. Age

Participant age will be calculated as the integer part of the number of years from date of birth to the date of signing the informed consent form, using the following formula:

Age = integer part of (date of informed consent – date of birth + 1) / 365.25

4.2.2. Body Mass Index

Body mass index (BMI) will be calculated as follows:

BMI $(kg/m^2) = [weight (kg)] / [height (m)]^2$

4.2.3. Prior and Concomitant Medication

Prior medication is defined as any nonstudy medication started before the first dose of INCB054707.

Concomitant medication is defined as any nonstudy medication that is:

- Started before the date of first administration of INCB054707 and is ongoing throughout the study or ends on/after the date of first administration of INCB054707.
- Started on/after the date of first administration of INCB054707 and is ongoing or ends during the course of study treatment.

A prior medication could also be classified as "both prior and concomitant medication" if the end date is on or after first administration of INCB054707. In the listing, it will be indicated whether a medication is prior-only, concomitant-only, or both prior and concomitant.

The start/stop dates recorded in the CRF by the investigator and his/her research staff will be used to identify when a concomitant medication was taken during the study. Any missing start date must be queried for resolution. Unresolved missing start dates will be handled as follows:

- If the date is completely missing, the medication will be considered both prior and concomitant.
- If only the day is missing, and the last day of the month is before the first dose date on Day 1, then the concomitant medication will be considered as starting before Day 1, and the incomplete date will be imputed as the last day of the month.
- If only the day is missing, and the first day of the month is after the first dose date on Day 1, then the concomitant medication will be considered as starting after Day 1, and the incomplete date will be imputed as the first day of the month.
- If only the day is missing, and the month is equal to the month of the first dose date on Day 1, then the incomplete date will be imputed as the first day of the month.
- If both the month and day are missing, and the last day of the year is before the first dose date on Day 1, then the concomitant medication will be considered as starting before Day 1, and the incomplete date will be imputed as if it is the last day of the

year. Otherwise, the incomplete date will be imputed as if it is the first day of the year.

5. STATISTICAL METHODOLOGY

5.1. General Methodology

Unless otherwise noted, SAS® software (SAS Institute Inc, Cary, NC; Version 9.1 or later) will be used for the generation of all tables, graphs, and statistical analyses. Descriptive summaries for continuous variables will include, but not be limited to, the number of observations, mean, standard deviation, median, minimum, and maximum. Descriptive summaries for categorical variables will include the number and percentage of participants in each category.

5.2. Treatment Groups

This is a multicenter, open-label, single-arm study. Participants will be summarized overall by total only.

5.3. Analysis Populations

5.3.1. Full Analysis Set

The FAS includes all participants enrolled in the study who received at least 1 dose of INCB054707.

The FAS will be used for the summary of demographics, baseline characteristics, participant disposition, and analyses of all efficacy and safety data.

6. BASELINE, EXPOSURE, AND DISPOSITION VARIABLES AND ANALYSES

6.1. Baseline and Demographics, Physical Characteristics, and Disease History

6.1.1. Demographics

The following demographics will be summarized for the FAS: age, sex, race, ethnicity, weight, height, and BMI.

6.1.2. Baseline Disease Characteristics

The following baseline disease characteristics will be summarized for the FAS:

- Days since first onset of HS
- Stable disease at least 90 days before screening (Yes/No)
- Other autoimmune disorders (Hyperlipidemia/Hypertension/Diabetes/Abdominal obesity/Arthritis/IBD: Crohn disease/IBD: Ulcerative colitis/Psoriasis/Spondylarthropathy/PCOS/Other/None)

6.1.3. Prior Therapy

Prior medication information for HS will be used to identify medication received by participants before enrollment into the study. Prior medications for HS will be summarized.

